Blood sampling for sparse PK of JNJ-3989 and optionally NA and PegIFN-α2a ⁱⁱ		X ^{jj}		X ^{jj,ll}		X ^{jj}			X ^{jj,ll}																
Blood sampling for intensive PK of JNJ-3989 and optionally NA and PegIFN-α2a (PK substudy) ^{kk}				X					X																
Exploratory Host Biomarkers																									
Whole blood RNA gene expression		X				X	X	X		X														X	
Whole blood single cell profiling		X			X	X				X		X	X	X			X			X				X	
Host serum proteins (eg, cytokines)		X		X	X	X		X	X	X		X	X	X			X			X				X	
Antidrug antibodies (to JNJ-3989 and optionally PegIFN-α2a)		X			X			X		X				X			X							X	
Immune Monitoring																									
Immune cells (PBMCs) (selected sites only) ^{mm}		X				X				X		X		X			X							X	
Pharmacogenomics (DNA)																									
HLA typing		X																							
Exploratory host genotyping (optional) ⁿⁿ		X																							
Epigenetic research (optional) ⁿⁿ		X				X				X		X		X			X							X	
Ongoing Participant Review																									
Concomitant therapy ^{oo}		X	X	X	X	X	X	X	X	X	X	X	X	X	X	X	X	X	X	X	X	X	X	X	X
Adverse events ^{oo, xx}		X	X	X	X	X	X	X	X	X	X	X	X	X	X	X	X	X	X	X	X	X	X	X	X

General Note: The ECGs should be completed before any tests, procedures or other consultations for that visit.

For Japan only, twice weekly visits are to be scheduled during the first week of treatment with PegIFN-α2a (ie, Week 12), followed by weekly visits up to Week 23, for assessment of safety (injection site reactions, physical examination, ophthalmic examination [when indicated], vital signs), hematology (only up to Week 20), concomitant

therapy and adverse events. During Week 12 (first 2 visits with PegIFN- α 2a), the study day visit window is +/-2d. After Week 12, the study day visit window is +/-3d until Week 24.

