AFP: alpha-fetoprotein; ALP: alkaline phosphatase; ALT: alanine aminotransferase; AST: aspartate aminotransferase; CKD-EPI: Chronic Kidney Disease Epidemiology Collaboration; CRF: case report form; CT: computed tomography; D/d: day; DAIDS: Division of Acquired Immunodeficiency Syndrome; DBP: diastolic blood pressure; DNA: deoxyribonucleic acid; ECG: electrocardiogram; eGFR: estimated glomerular filtration rate; EOS: end of study; EOSI: end of study intervention; FSH: follicle-stimulating hormone; FU: follow-up; GI = giga; HBe: hepatitis B core protein; HBe(Ag): hepatitis B e (antigen); HBcrAg: hepatitis B core-related antigen; HBs(Ag): hepatitis B surface (antigen); HBV: hepatitis B virus; HCC: hepatocellular carcinoma; HIV-1 (-2): human immunodeficiency virus type 1 (type 2); HLA: human leukocyte antigen; ICF: informed consent form; IgM: immunoglobulin M; INR: International Normalized Ratio; ISA: intervention-specific appendix; MRI: magnetic resonance imaging; NA: nucleos(t)ide analog; PBMC: peripheral blood mononuclear cells; PegIFN- α 2a: pegylated interferon alpha-2a; PK: pharmacokinetic; RBC: red blood cell; RNA: ribonucleic acid; SBP: systolic blood pressure; T4: thyroxine; TSH: thyroid stimulating hormone; ULN: upper limit of normal; W: week; WD: withdrawal.

- a. All study visits are to be scheduled relative to the baseline (Day 1) visit date. All follow-up study visits are to be scheduled relative to the Week 24/EOSI visit. An unscheduled visit can be performed upon the investigator's discretion, in case of HBV DNA elevations, ALT elevations, other signs of worsening of liver disease, or for any other reason.
- b. If necessary (eg, for operational reasons), the Screening Period may be extended up to a maximum of 8 weeks in agreement with the sponsor.
- c. Day 1 samples are to be collected before the first dose of study intervention.
- d. All assessments (with the exception of the sparse and intensive PK samples) should be performed before administration/intake of JNJ-3989 and NA. If applicable, weekly PegIFN- α 2a administration should preferably be done on the same day of the week in the evening by self-injection. If desired, participants can also choose to have the administration of PegIFN- α 2a performed on site irrespective of the time of day. For participants in Japan, weekly administration of PegIFN- α 2a must be performed at the study site by the investigator or his/her designee.

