^a Day 85 is the target day for the first administration of PegIFN- α 2a. Time interval [82-92] was selected to align the visit window with the protocol Schedule of Activities for Week 12. Any assessments performed before the administration of PegIFN- α 2a (date/time) at week 12 will be considered under treatment period 1 (Week 12 period 1) and assessments after the administration of PegIFN- α 2a (date/time) will be considered as treatment period 2 (Week 12 period 2).

^b End of treatment period 1 (EOT1) visit will be the last visit of treatment period 1.

^c End of treatment period 2 (EOT2) visit will be the last visit of treatment period 2.

b) Follow-up

Analysis phase	FU Target day	Analysis time point (Week)	Analysis time point (label)	Time interval (FU days)
Follow-up	15	26	Follow-up Week 2	[1, 22]
	29	28	Follow-up Week 4	[23, 43]
	57	32	Follow-up Week 8	[44, 71]
	85	36	Follow-up Week 12	[72, 99]
	113	40	Follow-up Week 16	[100, 127]
	141	44	Follow-up Week 20	[128, 155]
	169	48	Follow-up Week 24	[156, 183]
	197	52	Follow-up Week 28	[184,211]
	225	56	Follow-up Week 32	[212, 239]
	253	60	Follow-up Week 36	[240, 267]
	281	64	Follow-up Week 40	[268, 295]
	309	68	Follow-up Week 44	[296,323]
	337	72	Follow-up Week 48	[324, +∞]
	last visit in the study	999 ^a	EOS ^a	

^a End of study (EOS) visit (last available data during the follow-up phase) will be the last visit in the study.

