Thyroid Function Tests	Thyroid Stimulating Hormone (TSH) Thyroxine (T4)

Clinical laboratory tests will be summarized using safety analysis set for chemistry, hematology, urinalysis and renal biomarkers panels.

Descriptive statistics (n, mean, SD, minimum, median, and maximum) will be calculated for each laboratory parameter for observed values and changes from baseline at each scheduled time point by analysis phase.

Shift tables will be provided summarizing the shift in laboratory values from baseline over time with respect to abnormality criteria (low, normal, high) for each laboratory parameter by analysis phase.

Descriptive statistics and graphical displays will be presented for all chemistry, hematology, and urinalysis laboratory tests at scheduled time points.

Change from baseline over time will be summarized for chemistry, hematology, urinalysis tests, and renal biomarkers.

Abnormality criteria (based on the criteria specified in the DAIDS Toxicity Grading Scale (see Clinical Protocol Appendix 9, DAIDS Table) will be applied to baseline and postbaseline values or in accordance with the normal ranges of the clinical laboratory if no gradings are available.

Postbaseline abnormalities will be compared with their corresponding baseline result:

- For toxicity grades, treatment emergent will be concluded if the postbaseline grade is worse than the baseline grade.
- For abnormalities based on normal range and/or criteria: If the postbaseline value is above the upper limit and the baseline value is below the upper limit (eg, Normal or Low), then the postbaseline abnormality will be considered TE. The same applies to the postbaseline value being below the lower limit with the baseline value being above the lower limit (eg, Normal or High).
- If the baseline value is missing, a postbaseline abnormality will always be considered as TE.

For each lab parameter, a worst-case analysis will be performed by using the worst abnormality and/or worst toxicity grade lab value and time point per participant. The worst toxicity case is the value associated to the highest toxicity grade and is derived per parameter and toxicity direction (hypo / hyper). Worst-case will be derived within each analysis phase, including unscheduled assessments. For abnormalities, in case the same participant has both abnormalities (low and high)

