for the same lab test within the same phase, the participant will be counted in the analysis for both toxicity directions (abnormally high and low).

Imputation rules:

In case continuous laboratory results are not numerically expressed, but as a character (e.g. 'less than 2', '>25'), these results will be numerically imputed as follows:

- If the analysis result contains '<' then the result will be multiplied by 0.999 (e.g. <6.1 becomes 6.0939).
- If analysis result contains '>' then the result will be multiplied by 1.001 (e.g. >6.1 becomes 6.1061).
- If analysis result contains '≤' or '≥' then only the numeric portion of the result will be used.

This also applies to normal limits expressed as such.

Shift tables will be provided summarizing the shift in laboratory values from baseline over time with respect to abnormality criteria (low, normal, high) for each laboratory parameter by analysis phase.

The cross-tabulations of the worst toxicity grades over time versus baseline grade and the worst abnormalities versus baseline grade per parameter and per analysis phase will be presented also including the number of participants per worst grade and the number of participants per abnormality.

A tabulation of percentage and number of the participants who have treatment-emergent worst toxicity grades and treatment-emergent worst abnormalities per parameter and analysis phase will be included. The incidence table of worst toxicity grade abnormality in laboratory parameters will be also presented stratified by the subgroups of interest identified in Section 5.7.5.2.

Plots of mean (+/- SE) values and changes from baseline over time for selected laboratory parameters will be presented. Spaghetti-plots for selected laboratory parameters will be presented over time (with Week shown on x-axis).

A listing including all parameters with at least one treatment-emergent toxicity or abnormality per participant (exclusion of urinalysis) will be generated.

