5.7.5.2. Subgroups for Safety Analyses

Table 9: Subgroups for safety analyses

Subgroup	Definition
Sex	Male, Female
Age Group	≤ 45 years, > 45 years
Race	Asian, Non-Asian
BMI at Baseline	Underweight < 18.5 , Normal ≥ 18.5 - < 25 , Overweight ≥ 25 - < 30 , and Obese ≥ 30
Type of NA at Baseline	TeD, TAF, ETV

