6.3.1. Demographics

Table 11 presents a list of the demographic variables that will be summarized overall for the FAS.

Table 11: Demographic Variables

Continuous Variables:	Summary Type
Age (years)	Descriptive statistics (N, mean, standard deviation [SD], median and range [minimum and maximum], and IQ range).
Weight at baseline (kg)	
Height at screening (cm)	
Body Mass Index at baseline (BMI) (kg/m ²)	
Number of drinks containing alcohol (weekly period)	
Period of time using substances (beer, wine, distilled spirits) in months derived as = (stop date – start date +1)/30.4375; rounded to 1 decimal point	
Categorical Variables	Frequency distribution with the number and percentage of participants in each category.
Age (≤ 45 years, > 45 years)	
Sex (male, female, undifferentiated)	
Race ^a (American Indian or Alaska Native, Asian, Black or African American, Native Hawaiian or other Pacific Islander, White, Multiple)	
Ethnicity (Hispanic or Latino, not Hispanic or Latino)	
Country (Poland, Taiwan, Japan, New Zealand)	
BMI at baseline (underweight <18.5 kg/m ² , normal ≥18.5-<25 kg/m ² , overweight ≥25-<30 kg/m ² , obese ≥30 kg/m ²)	
History of tobacco use (Yes, No)	
Type of substance use (beer, wine, distilled spirits): current, former, never	

^a If multiple race categories are indicated, the Race is recorded as 'Multiple'

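### In Treatment Period 2, Japan-only hematology visits raise the expected worst-grade rate in the Asian column at equal toxicity; the race-stratified table needs a common-visit version

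*SAP*

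**What the plan says.** **Schedule.** In Protocol 1.3 (Schedule of Activities), hematology in Treatment Period 2 falls at Weeks 12, 14, 16, 20 and 24 for everyone. A general note adds visits in one country: "For Japan only, twice weekly visits are to be scheduled during the first week of treatment with PegIFN-α2a (ie, Week 12". From the next week on, the note asks Japanese sites for one visit per week, the last of these in Week 23. Hematology at these extra visits continues only to Week 20. Protocol Section 8 and the footnote in 8.1 put the planned blood volume at about 945 mL in general and about 985 mL in Japan, and attribute the difference to the added hematology.

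**Week 12 draw.** A footnote to the Schedule of Activities says: "All assessments (with the exception of the sparse and intensive PK samples) should be performed before administration/intake of JNJ-3989 and NA". SAP 5.1.3 places assessments made before the PegIFN-α2a injection in the first period: "at week 12 will be considered under treatment period 1 (Week 12 period 1".

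**Analysis.** SAP 5.6.3.1 takes the worst grade per participant and parameter: "Worst-case will be derived within each analysis phase, including unscheduled assessments". It adds: "The incidence table of worst toxicity grade abnormality in laboratory parameters will be also presented stratified by the subgroups of interest". Those subgroups are in SAP 5.7.5.2, where Race is "Asian, Non-Asian". SAP 6.3.1 lists "Country (Poland, Taiwan, Japan, New Zealand" as the country categories and gives no counts. Nothing in the SAP mentions the Japan-only draws.

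**The concern.** The worst of several values can only get worse as more values are taken. Here the number of values differs by country, and the table is split on a variable tied to country. Two groups with the same hematologic toxicity would then show different worst-grade rates, with the excess on the Asian side.

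The parameter matters in this trial. Hematologic abnormalities are events of special interest (Protocol 8.3.6), and added hematologic risk from combining PegIFN-α2a with the study agents is listed as a design-specific risk (Protocol 2.3.2.2.3). A reader who sees a higher Asian column in this table could take a scheduling artefact for a difference in tolerability.

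**Working it through.** The documents give no figure for this comparison, so there is none to reproduce.

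**1. Scheduled draws after the first PegIFN-α2a dose**
- Elsewhere: Weeks 14, 16, 20, 24 = 4.
- Japan: second Week 12 visit (1) + Weeks 13 to 20 (8) + Week 24 (1) = 10.
- The 6 extra draws fit the 985 − 945 = 40 mL of extra blood. No volume per draw is stated, so this supports the count but does not prove it.
- If the first Week 12 draw were also counted, the figures would be 11 and 5.

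**2. Chance that the worst draw reaches a given grade, same risk p per draw in both groups**

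For independent draws the chance is 1 − (1 − p)^k. At p = 0.05:
- k = 4: 1 − 0.95^4 = 18.5%
- k = 10: 1 − 0.95^10 = 40.1%

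For correlated draws I used a simulated Gaussian threshold model (400,000 persons, actual visit weeks). A person effect takes the stated share of the variance, and the rest follows an AR(1) process with weekly correlation 0.7. Moderate means a person share of 0.5; very high means 0.9. Both p and the correlations are assumptions.

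| p per draw | Independent: elsewhere vs Japan | Moderate | Very high |
|---|---|---|---|
| 0.02 | 7.8% vs 18.3% | 5.8% vs 8.7% | 3.6% vs 4.4% |
| 0.05 | 18.5% vs 40.1% | 13.1% vs 18.5% | 8.4% vs 9.9% |
| 0.10 | 34.4% vs 65.1% | 23.8% vs 31.4% | 15.7% vs 18.0% |
| 0.20 | 59.0% vs 89.3% | 41.2% vs 50.5% | 28.8% vs 32.1% |

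Japan is higher in every row.

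**3. From country to race**

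Let f be the Japanese share of the Asian group, and assume that all participants in Japan are Asian. The Asian-minus-Non-Asian gap is f × (Japan − elsewhere). At p = 0.05 and f = 0.5:
- independent: 0.5 × (40.1 − 18.5) = 10.8 points
- moderate: 0.5 × (18.5 − 13.1) = 2.7 points
- very high: 0.5 × (9.9 − 8.4) ≈ 0.8 points

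The documents do not give f. It falls as participants from Taiwan, who follow the common schedule, make up more of the Asian group.

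**4. After the fix**

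With Weeks 14, 16, 20 and 24 only, k = 4 in both groups and the expected gap at equal risk is 0.

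**The case against.** **The visit-window rule may already remove the extra draws.** SAP 5.1.3 keeps one visit per window for summaries. With the Table 4 windows that would leave at most 5 draws in Japan (Week 12 period 2, then Weeks 14, 16, 20, 24) against 4. But the same rule lets additional visits count for clinically important endpoints, and the specific sentence in 5.6.3.1 admits even unscheduled values. The specific sentence governs, or at best the two rules conflict.

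**Four is a scheduled minimum.** In every country a hematologic trigger leads to a confirmatory visit and, if confirmed, to weekly or biweekly visits (Protocol 8.3.6.6). This stands in part. It can narrow the gap in how severe the worst grade becomes once an abnormality has been found, and the calculation ignores it. It does not equalise the chance of finding the first abnormality.

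**The effect may be small and the table is descriptive.** This stands. SAP 5.1.7 plans no formal test. With an assumed 25 participants per race group, 2.7 points is 0.027 × 25 ≈ 0.7 of a participant. The standard error of the difference is about √(0.158 × 0.842/25 + 0.131 × 0.869/25) ≈ 10 points, where 15.8% is the average of 18.5% and 13.1%. The bias is systematic all the same, and it is cheap to remove.

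**Stronger readings that a reader might infer**
- *A doubling of the rate.* The ratio 40.1/18.5 ≈ 2.2 needs independent draws in one person a week apart, which is not realistic on continuous treatment.
- *The same bias in vital signs by race.* Japan does have more vital-sign visits, and SAP 5.6.3.4 uses a similar worst-case rule. But the sentence that orders subgroup stratification covers laboratory parameters only, and the SAP plans no race-stratified vital-signs table.
- *Distortion of the hematologic event-of-special-interest summary by race.* SAP 5.6.2 builds that summary from preferred terms, by phase and overall, not by race.

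**Conclusion.** The point holds for one table: the race-stratified worst-grade hematology table in Treatment Period 2. The draw counts, the worst-case rule and the race split are all in the documents, and together they push the Asian column upward at equal toxicity whenever the Asian group includes Japanese participants.

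The direction is well supported; the size is not known. It rests on an assumed risk per draw, an assumed within-person correlation and an unknown Japanese share. At 5% per draw with half of the Asian group in Japan, a realistic range is roughly 1 to 3 points, and 10.8 points is the independent-draw bound. Triggered repeat testing in all countries may reduce it further. The Japan-only note adds no chemistry tests, so those tables are not affected by scheduling in this way.

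**What to change.** In SAP 5.6.3.1, for the Treatment Period 2 hematology worst-grade table stratified by Race:
- add a version derived only from the scheduled visits common to all countries (Weeks 14, 16, 20, 24);
- keep the all-assessments version, overall and by race;
- footnote the Japan-only schedule on both;
- state that the worst-case rule takes precedence over the one-visit-per-window rule of SAP 5.1.3.

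The cost is a few lines of SAP text and one more run of an existing table. The downside is that the common-visit version omits abnormalities seen only at Japan-only visits, and those seen only at triggered unscheduled draws in any country. Both stay in the all-assessments table and the listings, so no toxicity is hidden. The common-visit version is the one to read across race columns; the all-assessments version is the one to read for total observed toxicity.

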5.6.3.2. Renal Safety

Renal safety parameters include the urine creatinine, serum creatinine, urine glucose total urine protein, total urine protein, total urine albumin, urine protein to creatinine ratio (UPCR), urine albumin to creatinine ratio (UACR), retinol binding protein (RBP), beta-2-microglobulin, RBP to creatinine ratio, beta-2-microglobulin to creatinine ratio, urine fractional excretion of phosphate (FEPO₄), Cystatin C, eGFR based on Creatinine (eGFR_{cr}), eGFR based on Cystatin C (eGFR_{cys}).

Descriptive statistics (n, mean, SD, minimum, median, and maximum) will be calculated for each parameter for observed values and changes from baseline at each scheduled time point by analysis phase. Descriptive statistics will also be calculated by subgroups (eGFR_{cr} Grade ≥ 3 [at least once during the treatment period] vs Grade < 3 , confirmed eGFR_{cr} Grade ≥ 3 , Type of NA at Baseline). The same analysis will be performed by eGFR_{cys} subgroups.

Plots of mean (\pm SE) values and changes from baseline over time for the renal safety parameters will be presented overall, and by subgroups (eGFR_{cr} Grade ≥ 3 [at least once during the treatment period] vs Grade < 3 , confirmed eGFR_{cr} Grade ≥ 3 , Type of NA at Baseline).

A confirmed eGFR_{cr} Grade ≥ 3 is defined as a Grade 3 or higher at 2 consecutive post-baseline measurements or an abnormality observed at 1 measurement followed by study drug discontinuation.

A listing including all renal safety parameters for participants with at least one treatment-emergent eGFR_{cr} Grade 3 or higher will be generated. Another listing will be generated with renal safety parameters for participants who had a confirmed eGFR_{cr} Grade 3 or higher.

5.6.3.2.1. eGFR

Stages of eGFR at baseline versus the minimum post-baseline eGFR value and the last available value will be summarized by count and percent of participants. Kidney disease stages are defined as follows: 1 (Normal): eGFR ≥ 90 ; 2 (Mild): eGFR 60-89; 3 (Moderate): eGFR 30-59; 4 (Severe): eGFR < 30 . This will be done for both eGFR_{cr} and eGFR_{cys}.

In addition to the above, the number and proportion of participants with a 10- $<$ 30%, 30- $<$ 50% and \geq 50% decrease from baseline will be tabulated.

Scatter plots of eGFR versus other renal biomarkers (total urine protein, total urine albumin, urine protein to creatinine ratio [UPCR], urine albumin to creatinine ratio [UACR], retinol binding protein (RBP) and beta-2-microglobulin, RBP to creatinine ratio and beta-2-microglobulin to creatinine ratio, and urine fractional excretion of phosphate [FEPO₄]) as well as spaghetti plots will be presented.

In addition, Cystatin C assessment is being performed as part of this study. eGFR_{cys} will also be calculated by using the CKD-EPI Cystatin C equation.

Differences between the two types of GFR calculation will be assessed. Cross-tabulation of eGFR_{cr} ($<$ 10%, 10- $<$ 30%, 30- $<$ 50% and \geq 50% decrease from baseline) versus eGFR_{cys} ($<$ 10%, 10- $<$ 30%, 30- $<$ 50% and \geq 50% decrease from baseline) will be presented over time.

5.6.3.2.2. Proximal Renal Tubular Function

Proteinuria by Quantitative Assessment

Total urine protein, total urine albumin, UPCR and UACR will be summarized by visit using descriptive statistics.

The number and proportion of participants with UACR and UPCR results in the following categories over time will be tabulated:

- UACR: < 30, ≥ 30 to 300, >300 mg/g
- UPCR: < 200 mg/g versus ≥ 200 mg/g

Median (Q1, Q3) percent change from baseline over time will be plotted.

The evolution over time of total urine protein and total urine albumin will also be presented.

Proteinuria by Urinalysis (Dipstick)

Treatment-emergent proteinuria by urinalysis (dipstick) over time will be summarized. Cross-tabulation of grades overtime versus baseline will also be presented.

Other Renal Biomarkers

Selected renal biomarkers RBP and beta-2-microglobulin, RBP to creatinine ratio and beta-2-microglobulin to creatinine ratio will be summarized by visit using descriptive statistics.

The number and proportion of participants with beta-2-microglobulin to creatinine ratio ≤343.5 µg/g and >343.5 µg/g will be tabulated over time.

The number and proportion of participants with retinal binding protein to creatinine ratio results in the following categories overtime will be tabulated:

- < 50 years of age: < 130 mcg/g creatinine, ≥ 130 mcg/g creatinine
- ≥ 50 years of age: < 172 mcg/g creatinine, ≥ 172 mcg/g creatinine

Phosphate excretion

Other renal biomarkers include FEPO4 that will be summarized by visit using descriptive statistics.

FEPO4 will be calculated as follows:

- Based on unadjusted serum creatinine:

$$\text{FEPO4 (\%)} = (\text{SCr} \times \text{UPO4}) / (\text{SPO4} \times \text{UCr}) \times 100 (\%)$$

Where SCr is serum creatinine concentration, UPO4 is urine phosphate concentration, SPO4 is serum phosphate concentration, and UCr is urine creatinine concentration.

The proportions of participants with FEPO4 $\leq 10\%$ and $>10\%$ will be tabulated.

The baseline, post-baseline, and change from baseline in FEPO4 will be summarized by visit using descriptive statistics. Median (Q1, Q3) change from baseline in FEPO4 over time will be plotted.

Subclinical renal proximal tubulopathy

Potential Markers of Renal Proximal Tubulopathy are:

1. Confirmed increase in serum creatinine ≥ 0.40 mg/dL from baseline.
2. Confirmed ≥ 2 grade level increase from baseline in graded proteinuria
3. Confirmed ≥ 1 grade level increase from baseline in graded hypophosphatemia
4. Confirmed ≥ 1 grade level increase from baseline in graded glycosuria concurrent with serum glucose ≤ 100 mg/dL (normoglycemic glycosuria)

A confirmed laboratory abnormality is defined as an abnormality observed at 2 consecutive post-baseline measurements or an abnormality observed at 1 post-baseline measurement followed by study drug discontinuation.

A subclinical renal proximal tubulopathy will be defined as confirmed abnormalities in any 2 out of the 4 renal parameters (serum creatinine and one or more of the 3 other markers of tubular dysfunction).

Baseline Subclinical renal proximal tubulopathy

Potential Markers of Renal Proximal Tubulopathy at Baseline

1. Grade ≥ 1 serum creatinine
2. Grade ≥ 2 proteinuria
3. Grade ≥ 1 hypophosphatemia
4. Grade ≥ 1 glycosuria concurrent with serum glucose ≤ 100 mg/dL (normoglycemic glycosuria)

A baseline subclinical renal proximal tubulopathy will be defined as abnormalities in 2 out of the 4 renal parameters (serum creatinine + 1 or more of the 3 other markers of tubular dysfunction).

